8.3 Statistical Analyses

The statistical testing will be conducted at the two-sided $\alpha = 0.05$ and 95% confidence interval (CI) will be computed, unless otherwise specified.

All p-values will be rounded to four decimal places. Statistical significance will be to be declared if the rounded p-value will be less than 0.05. Two-sided 95% CIs will be calculated.

Descriptive Statistics:

Descriptive statistics will be provided in summary tables according to the type of variable.

Continuous variables will be summarized by descriptive statistics (number of cases, mean, and standard deviation, median, minimum, and maximum). Categorical variables will be summarized using counts of patients and percentages.

Demographics and other baseline characteristics:

Demographic and baseline characteristics data will be summarized by means of descriptive statistics.

Demographic data, inclusion/exclusion criteria, general clinical data (medical history, vital signs and diagnosis, objective examination, and blood-chemical examinations) will be listed and presented in tables using only descriptive statistics. Inferential statistics will be applied only in case of evident discrepancies between the two treatment groups. A listing with the study treatment received by the patients will be made.

Since this study had two different time period, theses data could be listed by time period: period V1-V4 and V5-V6.

Concomitant treatments and rescue medication

Data of concomitant treatments and rescue medication will be coded and listed by treatment and study visit. Summary tables will be also produced on the frequencies of the reported treatments.

8.3.1 Primary Performance Analysis

In the analysis of primary performance variable, i.e. the mean difference from the baseline (delta) of the RSI score measured after 6 weeks of treatment, the two treatment groups will be compared using a Student's t-test for independent data.

The test results will be tabulated with the appropriate descriptive statistics and with the calculation of the 95% CI of the difference relative to the delta between the two study treatments.

The primary objective of the study will be achieved only if the statistically significant difference between the two study treatments with the current delta value will be coincident with that planned in the calculation of the numerosity, i.e. 3.6.

Sensitivity analyses will be conducted on the primary performance variable. The study of the temporal profile of the RSI questionnaire will be performed using the analysis of variance for repeated measures (ANOVA). In addition to the treatment effect, the time effect and the treatment by time interaction will be included in the model.

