- Patient's anamnesis, with brief details of medical history and particular attention to medical history of upper symptoms (i.e. date of onset, symptoms' description, frequency and intensity of symptoms);
- Anamnesis of concomitant therapies, treatments taken in the last 4 weeks and ongoing treatments, with particular attention to remote and recent therapies, intake of PPIs and/or medical devices and/or similar products (e.g. alginates, antacids, etc..), chronic use of drugs that interfere with the salivary secretion (e.g. anti-histamines or inhaled steroids) and thus represented an exclusion criterion and other non-permitted therapies;
- Objective examination and concomitant diseases;
- Haematology and blood chemistry: haemochrome, erythrosedimentation rate (ESR), C-reactive
 protein (CRP), aspartate aminotransferase (AST), alanine aminotransferase (ALT), alkaline
 phosphatase, gamma-glutamyl transpeptidase (gamma-GT), total and direct bilirubin, glycaemia,
 creatininemia, blood urea nitrogen (BUN) (tests performed in the last 3 months will be kept as
 valid);

- The evaluation of beta-human chorionic gonadotropin (beta-hCG) levels will be performed only in women of childbearing potential;
- RSI questionnaire, completed by patients following the Investigator's explanation;
- Likert scale, completed by patients following the Investigator's explanation.

Furthermore, the Investigator:

- Explained to patients which other products could or not could be taken for the entire study duration;
- Dispensed a diary to patients, to be completed daily, explaining to patients the procedures for completion and the importance of a correct filling, recommending them to daily report the presence and intensity of upper symptoms, the amount of taken investigational product, the possible use of other products taken on-demand for the treatment of GERD and of all other products, the possible changes of dose of taken treatments and all possible adverse events or incidents occurred during the study.

Patients satisfying inclusion/exclusion criteria and that, by signing the informed consent provided at the beginning of the study, accepted to adhere to the study procedures and to complete the daily diary, will be included in the study and will be randomly allocated to the investigational product to be taken for the following 6 weeks of treatment. Thus the Investigator proceeded to:

- Patient's randomisation and assignment of a randomisation number;

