7.5 Data Management

As said above, computer systems used for remote data collection and the system for data storing and processing will be validated. Verification and cross-verification of the data entered by the study personnel at each visit will be automatically performed by the system, according to predefined nature/type of the data, value ranges and rules. All rules applied by the system to check specific items will be detailed in a document issued by the Data Management service of the CRO. Queries will be automatically generated by the system for all data found to be inconsistent, incorrect or missing. Queries to be solved/unclear data to be corrected (or confirmed) will be highlighted by the system, to be easily identified by the study personnel when accessing the eCRF website. All changes performed by the Investigator will be tracked by the system.

Once all data will be entered in the eCRF and all outstanding queries will be solved, the Monitor of the study authorized the Investigator to "freeze" the data of the subject's eCRF. No change will be accepted by the system after freezing. Nonetheless, it could have been still necessary to edit additional queries following general quality control checks performed by the Data Manager of the study on the frozen database: in case, queries will be to be edited in paper form and referred to the appropriate hospital/study site personnel, to be resolved with assistance of the study Monitors.

When all data will be received, all data problems will be resolved, all data checks and quality control checks will be performed, and a data review meeting will be held, the trial database will be considered clean and could be locked. After database lock, the appointed statistician performed the statistical analysis as planned. Any further modification of recorded data will be to be documented in a database log form.

The data of all patients, recorded on the eCRFs and on the patient diaries, will be stored in a suitable, properly designed database.

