8 STATISTICAL METHODS

The statistical methods will be planned in the protocol and will be then updated, agreed and approved in the final Statistical Analysis Plan (SAP), version 1.1, dated 19 February 2019 (Annex 10).

Statistical analysis will be performed by the statistical department of High Research S.r.l., [name].

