8.1 Sample Size Justification

Although a search in literature has not identified any published article for trials that used the same investigation design as that used in the present study, some recently published articles (9, 13-15) allowed to formulate a sample size calculation for the present investigation.

The calculation of the sample size will be based on the primary objective of the investigation, i.e. to assess the change of RSI questionnaire from baseline to 6 weeks of treatment in the two treatment arms, Gerdoff®- PPI and PPI alone, based on an hypothesis that the addition of Gerdoff® to PPI could improve the effect of disappearance and of rapidity of control of upper symptoms of GERD. Such effect will be evaluated as the mean change in RSI compared to baseline, taking into consideration the variable age, standard deviation (SD) and expected value after treatment with omeprazole.

The following assumptions will be made for the sample size calculation:

Difference between the two arms (delta): 3.6; SD of the difference: 5.

Based on these assumptions, for a comparison based on unpaired Student t test, at a power of 80% and a level of probability of 5% for a two-tailed test, 62 patients (31 in each treatment arm) will be to be included in the study. Estimating a drop-out rate of 20%, 78 patients (39 in each treatment arm) will be to be included in the study.

The software PS Power and Sample Size Calculations Version 3.0, January 2009, will be used for the sample size calculation.

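### The primary t-test on RSI change is valid, but an ANCOVA with baseline RSI as covariate would use data already collected, probably with more precision and at almost no cost

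*Combined protocol and SAP*

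**What the plan says.** Section 6.5.3 defines the primary variable as the change in total RSI score (range 0 to 45) from baseline to V4. For its analysis, section 8.3.1 states that "the two treatment groups will be compared using a Student's t-test for independent data", with a 95% CI for the difference. The sample size in section 8.1 is derived "for a comparison based on unpaired Student t test, at a power of 80"%, with the inputs "Difference between the two arms (delta): 3.6; SD of the difference: 5". This gives 31 per arm and, after 20% drop-out, "78 patients (39 in each treatment arm) will be to be included in the study".

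Baseline RSI is available for everyone. A score of at least 20 is an entry criterion (section 6.3.1), and the V1 procedures in section 6.5.2 include the "RSI questionnaire, completed by patients following" the investigator's explanation, before randomisation.

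Nothing in the supplied text uses that score as a covariate. The repeated-measures ANOVA in section 8.3.1 contains treatment, time and their interaction only. Section 6.4.7 describes balanced blocks and mentions no stratification by RSI. Section 8 says that the methods are "updated, agreed and approved in the final Statistical Analysis Plan (SAP), version 1.1" (Annex 10). That document was not supplied, so this point concerns section 8.3.1 as written.

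**The concern.** The unadjusted comparison does use baseline RSI, because the change score subtracts it, but only with a fixed slope of 1. If the true slope of V4 on baseline differs from 1, the change score carries variation that baseline RSI could have explained. ANCOVA estimates the slope, so its population residual variance cannot exceed that of the change score.

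At stake are power and the width of the confidence interval in a small trial planned at only 80% power. The validity of the test is not in question. With about 31 patients per arm and no stratification by RSI, some chance imbalance in baseline severity is to be expected. That is not a bias on average, but ANCOVA adjusts the realised estimate for it and the t-test on change does so only through the fixed slope.

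**Working it through.** **Inputs from section 8.1.** Difference 3.6; SD 5, read as the SD of the change score within each arm, which is the reading that reproduces the stated sample size; two-sided 5%; 80% power; 31 evaluable or 39 randomised per arm. The standardised difference is 3.6/5 = 0.72.

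**The plan's own figure.** n per arm = 2 × [5 × (1.960 + 0.842)/3.6]² = 30.28, rounded up to 31, so 62 in total. Drop-out: 62/0.8 = 77.5, rounded up to 78. Both figures reproduce. The exact noncentral-t power of the t-test is 79.6% at 31 per arm and 88.1% if all 39 per arm are analysed.

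**Assumptions not in the documents.** Let rho be the baseline-V4 correlation and k the baseline SD divided by the V4 SD. I take rho = 0.3, 0.5, 0.6 and k = 1, 0.8, 0.6, with k = 0.5 as a further check. These ranges are illustrative, not bounds.

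**Formulas.**
- Residual variance of ANCOVA relative to the change score: ratio = (1 − rho²)/(1 + k² − 2·rho·k). It equals 1 only when rho = k and is smaller otherwise.
- ANCOVA power: noncentral t with 2n − 3 degrees of freedom and noncentrality 0.72/√ratio × √(n/2)/√(1 + 1/(2n − 5)). The last factor allows for chance baseline imbalance.
- CI half-width: t(0.975, df) × 5 × √ratio × √(2/n), times √(1 + 1/(2n − 5)) for ANCOVA. For the t-test, ratio = 1 and df = 2n − 2.

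**Worked cell.** With k = 1, rho = 0.5 and n = 31: ratio = 0.75/1 = 0.750. The noncentrality rises from 0.72 × √15.5 = 2.835 for the t-test to 2.835/√0.750/√(1 + 1/57) = 3.245, which gives 89.1% power.

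**Results for rho = 0.3 / 0.5 / 0.6.**

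| k | Variance ratio | ANCOVA power, 31 per arm (t-test 79.6%) | ANCOVA power, 39 per arm (t-test 88.1%) |
|---|---|---|---|
| 1.0 | 0.650 / 0.750 / 0.800 | 92.9 / 89.1 / 87.1% | 97.2 / 94.9 / 93.6% |
| 0.8 | 0.784 / 0.893 / 0.941 | 87.7 / 83.3 / 81.3% | 94.1 / 91.0 / 89.5% |
| 0.6 | 0.910 / 0.987 / 1.000 | 82.6 / 79.5 / 78.9% | 90.5 / 88.1 / 87.6% |
| 0.5 | 0.958 / 1.000 / 0.985 | 80.6 / 78.9 / 79.5% | 89.0 / 87.6 / 88.1% |

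The CI half-width at 31 per arm is 2.54 RSI points with the t-test and 2.07 to 2.56 with ANCOVA. At 39 per arm it is 2.26 against 1.83 to 2.27.

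**Worst case (rho = k).** ANCOVA loses 0.7 power points at 31 per arm and 0.4 at 39. Hardly any of this is the lost degree of freedom, which alone takes power from 79.65% to 79.62% at 31 per arm. The rest is the chance-imbalance factor.

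**Simulation.** With 40,000 trials in each of the nine cells for k = 1, 0.8 and 0.6, power at 31 per arm was 79.2% to 80.0% for the t-test and 79.0% to 92.9% for ANCOVA. At 39 per arm it was 88.1% to 88.4% and 87.8% to 97.3%. Separate runs at 31 per arm with k = 1 gave a type I error of 4.9% to 5.1% for both tests.

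**The case against.** The strongest reply is that nothing here is broken. Endpoint, sizing test and analysis agree with one another, and 31, 62 and 78 are right for the test chosen. That stands, and this point is an improvement to a valid analysis.

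Second, the gain depends on two quantities that the documents do not give, and the largest figures need k near 1. The entry floor of RSI 20 narrows the baseline spread and makes k below 1 plausible. At k = 0.5 to 0.6 the change in power at 31 per arm runs from −0.7 to +3.0 points (78.9% and 82.6% against 79.6%). This also stands: the gain is plausible but not assured.

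Third, section 8.3.1 counts the objective as achieved only if the significant difference "will be coincident with that planned in the calculation of the numerosity, i.e. 3.6". If that means significant with an observed difference of at least 3.6, the chance of success at a true difference of 3.6 is about 50% with either test (49.5% to 50.6% in all 18 simulated cells). Under that reading, ANCOVA improves only the precision of the estimate, and the powers above describe significance alone.

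Fourth, it may be too late. The trial is open-label. Section 7.5 says that "a data review meeting will be held" before database lock, and section 8.2 describes a decision of that meeting in the past tense. Tenses are mixed throughout the document, and the text does not say that data were reviewed by arm, so this is not settled. It does determine which form of the fix applies.

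What remains after these points is a lopsided trade-off: at most about 0.7 power points lost within the assumed range, against up to about 13 gained (92.9% − 79.6%).

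**Conclusion.** The point holds as a recommendation on efficiency. The supplied text analyses RSI change without an estimated baseline slope, although baseline RSI is available for every eligible patient. Under the assumed rho of 0.3 to 0.6 and k of 0.6 to 1.0, ANCOVA moves power for a significant difference from 79.6% to between 78.9% and 92.9% at 31 per arm, and from 88.1% to between 87.6% and 97.2% at 39 per arm. The benefit is appreciable when k is near 0.8 to 1 and close to nil when k is near 0.5 to 0.6. Confidence in its size is medium, because rho and k are assumptions and SAP version 1.1 has not been seen.

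**What to change.** If no one has yet reviewed data by arm, make the primary analysis an ANCOVA of RSI change at V4 with treatment and continuous baseline RSI. Report the adjusted difference with its 95% CI as the primary estimate and keep the t-test as supportive. Make section 8.3.1 and SAP version 1.1 state the same primary analysis.

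If data have already been reviewed by arm, leave the t-test as primary and report the ANCOVA as a sensitivity analysis, labelled as added later. Switching the primary test at that stage in an open-label trial would itself invite criticism.

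The cost is an edit to the protocol and SAP text and a few lines of code. No new data are needed and the sample size need not change. The statistical price is one degree of freedom plus the small allowance for chance imbalance.

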3 INVESTIGATORS AND STUDY ADMINISTRATIVE STRUCTURE

The investigation will be conducted in 2 investigational sites in Italy. One more site in Italy will be opened, but no patients will be enrolled in this site.

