6 CLINICAL INVESTIGATION PLAN

6.1 Overall Study Design

This will be a phase III, multicentre, prospective, randomised, open-label, two-parallel groups study, followed by a follow-up period.

[figure not shown]
The study plan included a 6-week treatment period, from visit V1 to visit V4, of first-diagnosis patients presenting upper symptoms related to diagnosis of GERD, in the presence/absence of typical symptoms. Patients will be randomised to receive an open-label treatment (in a 1:1 ratio) with Gerdoff®- omeprazole (PPI) (Group 1) or omeprazole (PPI) alone (Group 2). The first administration of investigational products started in the morning of the day following visit V1.

At visit V4, patients in Group 2 who will be treated with omeprazole (PPI) alone, and patients in Group 1 who will be treated with Gerdoff®- omeprazole (PPI) and will be classified as non-responder, completed the study and the most appropriate therapy to treat their symptoms will be prescribed by the investigator.

To assess the maintenance of the effects of treatment, at visit V4 (end of study visit), patients in Group 1 who will be treated with Gerdoff®- omeprazole (PPI) and will be classified as responders could continue with a 12-week follow-up period. During the follow-up period patients could be randomly assigned as open-label (in a 1:1 ratio) to treatment with Gerdoff® or to a control group, which will not receive any treatment. To safeguard the health and well-being of patients, and to keep under control the possible upper symptoms of GERD that could appear, all patients that continued in the follow-up period received omeprazole as rescue medication in a quantity adequate to cover the entire follow-up period. This therapy will be chosen by the study coordinator as it is the treatment commonly used in clinical practice for the treatment of all specific and non-specific symptoms of GERD. The investigator explained to patients that rescue omeprazole could be taken only if necessary and according to the indications given by the Investigator, at constant dosage, and that use will be to be recorded in the daily diary by indicating the reason for administration. The investigator had to report the data in the source documents and in the electronic case report forms (eCRF).

A schematic diagram of the study design follows (Figure 1):

Figure 1. Study diagram

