6.4.7 Treatment Allocation and Randomisation

All patients that accepted to take part in the study and freely signed the informed consent received an individual progressive screening number. Following the verification of all inclusion and exclusion criteria, a progressive randomisation number will be assigned to patients, which identified the patient for the entire study duration.

The randomization list will be in balanced-block design and will be prepared using a validated system that automates the random assignment of treatment groups to randomization numbers. Randomisation will be performed as a function of lists produced for the study, which provided the correct sequence

for the assignment of patients to the study groups and for the dispensation to patients of the treatment scheduled for the assigned group and as a function of the phase of the study.

In case of screening failure or study discontinuation, the screening and randomisation number could not be re-assigned to another patient and the patient will be not allowed to re-enter the study. Similarly, in case that a patient interrupted the participation in the study after the randomisation but before the start of use of the kit of the investigational product, this kit could not be assigned to another patient.

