6.5.3 Study Endpoints

Primary performance variable

The primary performance variable of the study will be the change from baseline to visit V4 of the total score of RSI questionnaire, used to assess the effect of treatment on upper symptoms. The RSI questionnaire examines 9 items, to be scored from 0 to 5, with a higher score indication a higher severity of the symptom (range of total score: 0-45).

Secondary performance variables

The secondary performance variables of the study will be:

- Change of the total score of RSI questionnaire from baseline to the other time points;
- Change of the score of single items of the RSI questionnaire from baseline at any time point;
- Number and percentage of responder/non-responder patients at end of treatment (visit V4);
- Change from baseline to end of treatment (visit V4) and end of follow-up (visit V6) of upper symptoms, assessed using the Likert scale. The Likert scale scored symptoms from 0 to 4, with a higher score indication a higher frequency of the symptom;
- Presence of upper symptoms at baseline, end of treatment (visit V4) and end of follow-up (visit V6), assessed using the RSI questionnaire and the Likert scale:
- Use of rescue medication during the follow-up period: administered therapy, frequency of administration, timing of administration and administered dose;
- Patient's opinion of satisfaction with treatment, requested at intermediate Visits V2 and V3, and at the end of treatment visit V4, by means of a semiquantitative ordinal scale, where: 0 = low, 1 = discrete, 2 = good, 3 = excellent.

Safety variables

The safety variables of the study will be:

- Frequency of adverse events and incidents occurring at any time, during the study;
- Changes from baseline of haematology and blood chemistry parameters;
- Changes from baseline of vital signs (weight, BMI, blood pressure, heart rate and respiratory rate).

Incidents and adverse events

Incidents

According to MEDDEV 2.12.1, Rev. 8, a medical device incident is defined as 'any malfunction or deterioration in the characteristics and/or clinical performance of a device, as well as any inadequacy in the labelling or the instructions for use, which, directly or indirectly, might lead to or might have

led to the death of a patient, or a user or of other persons or to a serious deterioration in their state of health'.

A medical device incident that required reporting included:

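### Two sites enrol, but the primary t-test on RSI change has no site term: a possible, cheaply avoided loss of precision

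*Combined protocol and SAP*

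**What the plan says.** Section 3: "The investigation will be conducted in 2 investigational sites in Italy". A third site is mentioned, but it contributes no data: "One more site in Italy will be opened, but no patients will be enrolled in this site".

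Section 6.4.7 on allocation: "The randomization list will be in balanced-block design". It goes on: "Randomisation will be performed as a function of lists produced for the study, which provided the correct sequence", and links the lists to the assigned group and to the study period ("as a function of the phase of the study"). It names no stratification factor. It neither says that each site has its own list nor rules this out, and it gives no block size.

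Section 6.5.3 defines the primary variable as the "change from baseline to visit V4 of the total score of RSI questionnaire". Section 8.3.1 tests it with a "t-test for independent data" and reports a 95% CI for the difference. The repeated-measures ANOVA in the same section contains treatment, time and their interaction only. Nowhere in Section 8 is there a site covariate, a by-site summary or a check of treatment by site.

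**The concern.** When patients come from two clinics, part of the spread in RSI change may simply reflect which clinic they attended. An unadjusted t-test counts that part as random error, although a single model term could remove it.

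Some features of the plan make a site difference conceivable. The RSI is completed by the patient after the local investigator's explanation, treatment is open-label, and the route to diagnosis through an ENT specialist follows each site's usual practice (Section 6.5.2). None of this shows that a difference exists.

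The evaluable sample of 31 per arm in Section 8.1 is set at the 80% power target, so precision that costs almost nothing to recover is worth having. The allocation text adds a second question. If the lists were made per site, an analysis that ignores site does not match the randomisation, and its standard error is too large whenever the sites differ.

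**Working it through.** **Inputs from the documents.** Difference 3.6, SD 5, two-sided 5%, 80% power, 31 evaluable per arm (62), 20% drop-out, 39 enrolled per arm (78): Section 8.1. Two enrolling sites: Section 3.

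**Inputs assumed.** The difference D between sites in mean RSI change, and the share p of patients at one site. The documents give neither, so a range is shown.

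**1. The plan's own figure.** n per arm = 2 × 5² × (1.960 + 0.842)² / 3.6² = 30.3, rounded up to 31, or 62 in all. With drop-out, 62 / 0.80 = 77.5, rounded up to 78. Both stated figures reproduce when 5 is used as the common SD of RSI change. By the noncentral t distribution with 60 df, power at 31 per arm is 79.6%. The planned standard error is 5 × √(2/31) = 1.27 points.

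**2. How much of the variance is site.** Site variance = p(1 − p)D². Within-site SD = √(25 − p(1 − p)D²). Power is then recomputed with that SD and 59 df, with site balanced across arms.

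| D (RSI points) | Site variance, 50:50 | Share of 25 | Within-site SD | Power with site, 50:50 | Power with site, 70:30 |
|---|---|---|---|---|---|
| none | 0 | 0% | 5.00 | 79.62% | 79.62% |
| 1 | 0.25 | 1% | 4.975 | 80.0% | 80.0% |
| 2 | 1.00 | 4% | 4.899 | 81.2% | 81.0% |
| 3 | 2.25 | 9% | 4.770 | 83.2% | 82.6% |
| 4 | 4.00 | 16% | 4.583 | 86.0% | 85.0% |

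Without the site term, power is 79.65% in every row. At D = 2, a split of 80:20 gives 80.6% and 90:10 gives 80.2%.

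**3. If 5 is the SD within a site.** The total SD is then √(25 + p(1 − p)D²), and at a 50:50 split the planned unadjusted test has power 79.3%, 78.1%, 76.2% and 73.6% for D = 1, 2, 3 and 4.

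**4. Lists not made per site.** The site mix can then differ between arms by chance. At a 50:50 split and 31 per arm, the chance contribution to the arm difference has SD of about D × √(0.25 × 2/31): 0.25, 0.38 and 0.51 points for D = 2, 3 and 4. This is already one component of the 1.27-point standard error in step 1 and is not to be added to it. In a simulation of 62 patients in blocks of 4 (block size assumed; 8,000 runs per setting), the type I error of the unadjusted test was 4.8% to 5.3% for D = 2, 3 and 5.

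**5. Lists made per site.** In the same simulation with blocks within site, the type I error of the unadjusted test was 4.9% at D = 2, 3.9% at D = 3 and 2.2% at D = 5. With site in the model it was 5.2%, 4.7% and 4.8%. The Monte Carlo standard error is √(0.05 × 0.95 / 8000) = 0.24 percentage points, so the drop is clear at D = 3 and 5 and not visible at D = 2.

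**The case against.** The strongest reply is that the planned test is valid and the gain may be trivial. Validity stands: the t-test is unbiased, and its error rate is near 5% or below under either way of making the lists.

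The reply on size partly stands. A site difference is not documented, and there are reasons to expect a small one. The endpoint is a change from baseline, so stable differences in how the questionnaire is explained largely cancel. Patients complete a validated Italian version (Section 2.1). The sites share the RSI entry threshold (Section 6.3.1) and an investigator meeting on procedures (Section 7.1). With D of 1 or 2 points, or a very uneven split, the gain is below two percentage points.

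Three stronger readings are tempting, and the documents do not support them.

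- A reader might infer that randomisation ignores site. Section 6.4.7 is silent on this; the plural lists may refer to sites or to the two study periods.
- A reader might infer that chance site imbalance biases the result. It does not: without stratification that variation is already inside the standard error.
- A reader might infer that the sample has no slack at all. If V4 data were obtained on all 39 enrolled per arm, power under the plan's assumptions would be 88.1%; at 35 per arm it would be 84.4%.

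A further caution concerns the remedy. In an open-label trial each site sees its own past allocations, so separate blocked lists per site with small fixed blocks would make the next assignment easier to guess. Per-site lists are therefore not a cost-free improvement. Lastly, if expectation effects differed by both arm and site, that would be an interaction, which a site main effect does not address.

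**Conclusion.** The point holds as a cheap improvement in precision. The omission of site from the primary analysis is documented; whether the randomisation uses site is an open question for the sponsor.

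At 31 per arm, a total SD of 5 and an even split, the benefit is about 0.4 and 1.6 percentage points of power for site differences of 1 and 2 RSI points, and about 3.6 and 6.4 points for 3 and 4. It shrinks with an uneven split. All of these rest on an assumed site difference. The case for the term does not depend on the answer about the lists: without per-site lists it recovers precision, and with them it also brings the test and interval back to their nominal level.

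**What to change.** In Section 8.3.1, replace the t-test with a linear model of baseline-to-V4 RSI change with treatment and site as fixed factors. Report the adjusted treatment difference with its 95% CI as the primary result. Specify this before database lock; it can be done even if the randomisation lists already exist.

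The cost is one degree of freedom (60 to 59 at 31 per arm). If the sites do not differ, power goes from 79.65% to 79.62%, and the sample size need not change.

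In Section 6.4.7, state whether the lists are made per site. If they are, use varying block sizes that are concealed from the sites, because the trial is open-label. If they are not, the model term alone is enough, and nothing here requires changing the lists.

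### The success rule ties the primary objective to an observed difference of 3.6, so the stated 80% power falls to about 50% at most when the planning assumption is exactly true

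*Combined protocol and SAP*

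**What the plan says.** Section 8.1 sets out the planning assumptions: "Difference between the two arms (delta): 3.6; SD of the difference: 5". The calculation is made "for a comparison based on unpaired Student t test", and the result is "at a power of 80% and a level of probability of 5% for a two-tailed test, 62 patients (31 in each treatment arm"). Allowing for 20% drop-out, this becomes 78 patients, 39 per arm. No other condition for success enters the calculation.

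Section 8.3 sets two-sided testing at 0.05. In Section 8.3.1, "the two treatment groups will be compared using a Student's t-test for independent data", with a 95% CI for the difference. The section then adds a rule for success. It opens "The primary objective of the study will be achieved only if the statistically significant difference between the two study treatments" and continues "with the current delta value will be coincident with that planned in the calculation of the numerosity, i.e. 3.6".

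Section 8.3.1 gives no tolerance around 3.6, no wording such as at least, and no link between the CI and success. Elsewhere, 3.6 appears only in Section 8.1, as a sample-size assumption.

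**The concern.** The trial is powered for one decision rule and judged by another. The 3.6 in Section 8.1 is the assumed true effect. Section 8.3.1 turns it into a condition on the estimate, taking the current delta to mean the observed difference.

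Read literally, a significant difference of 3.0 fails, and so does a significant difference of 5.0, although the latter shows a larger benefit than planned. Read generously, as at least 3.6, the rule asks an unbiased estimate of a true 3.6 not to fall below its own target, which it does half the time at any sample size.

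The label attached to the whole trial is at stake. A product that works exactly as assumed would be declared a failure in at least half of such trials, many of them with p below 0.05. The wording also leaves room to choose a reading after the result is known, and that choice would be hard to defend in an open-label trial.

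**Working it through.** **Inputs.** Difference 3.6, SD 5, two-sided 5%, power 80%, 31 evaluable per arm and 39 randomised per arm (Section 8.1); 1:1 allocation (Section 6.1); unpaired t test (Sections 8.1 and 8.3.1). The SD of 5 is taken as the per-arm SD of the change score, because that reading reproduces the plan's sample size.

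**1. The plan's own figure.** By the normal approximation, n per arm = 2 × (1.960 + 0.8416)² × 5² / 3.6² = 30.3, rounded up to 31, so 62 in total. For drop-out, 62 / 0.8 = 77.5, rounded up to 78. Both figures reproduce. Power at 31 per arm is 80.9% by the normal approximation and 79.7% by the noncentral t. The stated 80% is therefore the power of significance alone.

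**2. Smallest significant difference.** At 31 per arm, SE = 5 × √(2/31) = 1.270. With the t critical value 2.00 (60 df), a difference of about 2.54 is significant. At 39 per arm, SE = 5 × √(2/39) = 1.132 and the limit is about 2.26.

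**3. Reading the rule as at least 3.6.** With a true difference of 3.6, the estimate is symmetric about 3.6, so P(estimate ≥ 3.6) = 0.50 whatever the sample size. Nearly all such estimates are significant, since 3.6 is well above 2.54. The joint probability is therefore 50.0% at both sizes.

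The probability of a significant result that still fails is approximately 0.5 − Φ((2.54 − 3.6)/1.270) = 0.5 − Φ(−0.835) = 0.5 − 0.202 = 29.8%. Simulation, which also lets the sample SD vary, gives 29.7% at 31 per arm. At 39 per arm it is 88.1% − 50.0% = 38.1%, so a larger trial produces more significant failures.

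**4. Other readings.** True difference 3.6, SD 5, 1,000,000 simulated trials:

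| Rule for success | 31 per arm | 39 per arm |
|---|---|---|
| Significant (the rule used for sizing) | 79.7% | 88.1% |
| Significant and estimate ≥ 3.6 | 50.0% | 50.0% |
| Significant and estimate equals 3.6 to one decimal | 3.1% | 3.5% |
| Significant and within 0.5 of 3.6 | 30.7% | 34.2% |
| Significant and within 1.0 of 3.6 | 55.5% | 62.3% |
| Significant and 95% CI contains 3.6 | 77.3% | 85.6% |
| Lower 95% limit above 3.6 | 2.5% | 2.5% |

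**5. Larger true effects.** For 80% success under the at-least-3.6 rule, the true difference would have to be 3.6 + 0.8416 × 1.270 = 4.67 at 31 per arm, or 3.6 + 0.8416 × 1.132 = 4.55 at 39 per arm. A matching rule runs the other way: with a 0.5-point tolerance and 31 per arm, success falls from 30.7% at a true 3.6 to 5.6% at a true 6.0.

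**6. Sensitivity to the SD.** For SDs from 4 to 7, success under the at-least-3.6 rule stays between 47.7% and 50.1%.

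**The case against.** The strongest reply is that the sentence is poorly worded and that looser readings do better than 50%. If the estimate need only lie within 1.0 point of 3.6, success is 55.5% at 31 per arm. If the 95% CI must contain 3.6, it is 77.3%, and the CI is mentioned just before the rule. The arithmetic is right. But Section 8.3.1 states neither a tolerance nor a CI criterion, and at 31 per arm both readings still fall short of the 79.7% for significance alone. If only significance was meant, the reference to 3.6 has no function, yet it sits inside a condition that must be met.

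Requiring significance plus a minimum observed effect is also a legitimate, stricter rule. It does not inflate type I error: with no true effect, the chance of a significant difference of at least 3.6 is 0.23% at 31 per arm. This stands, but such a rule has to be stated as a minimum and its power reported, and the plan does neither.

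The estimate, test and CI will be tabulated whatever the rule says, so only the verdict on the primary objective is at risk. That is true, but this verdict is what the sentence exists to settle.

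Finally, Section 8 refers to a SAP version 1.1 in Annex 10, whose separate text is not in the document reviewed. It may repeat or clarify the sentence; that cannot be checked here. It does not cure Section 8.3.1 as written.

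**Conclusion.** The concern holds. The rule in Section 8.3.1 is not the one for which Section 8.1 calculated 80% power. With a true difference of exactly 3.6, the two direct readings give at most about 50% success: 50.0% if 3.6 is a minimum for the estimate, and about 3% if the estimate must equal it. The 50% follows from symmetry, so neither sample size nor any plausible SD rescues it. The exact percentages rest on approximately normal mean differences and on 5 being the per-arm SD of the change score. Readings above 50% need a criterion that the plan does not contain. Because the sentence decides whether the trial succeeds, it must be corrected.

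**What to change.** Replace the sentence in Section 8.3.1 with wording such as:

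> The primary objective is achieved if the two-sided t test at the 0.05 level shows a greater mean reduction in RSI with Gerdoff plus PPI than with PPI alone. The value 3.6 is a planning assumption; the estimated difference and its 95% CI will be reported and discussed against it.

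This brings the success rule into line with Section 8.1, and the existing sample size stands.

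If the sponsor does want a minimum observed effect, the rule should say at least 3.6, and Section 8.1 should give its power as about 50% at a true difference of 3.6. More patients will not raise that figure. 80% would require a true difference of about 4.67 with 31 evaluable per arm.

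The cost is one sentence, carried into the SAP annex if it repeats the rule, with no extra patients or data. The change should be dated and justified before the results are known. It makes success easier to declare, Section 6.6 foresees no amendments, and Section 8.2 already reports a decision from the data review meeting. If the change comes after data review, the superseded rule should be disclosed with the result.
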